Aim 1 (Strategy 1): Modulating the limbic system as an approach to treatment: mPFC iTBS. Cigarette smokers will be randomized to receive 10 days of real iTBS or sham iTBS directed to the mPFC. Intermittently the desire to smoke, cigarette value using behavioral economic demand, preference for immediate gratification (delay discounting), and cigarette self-administration will be assessed. Smoking cue-evoked brain activity will also be measured when individuals are asked to 'crave' (passive limbic engagement) versus 'resist' the craving (executive engagement)(7,11-13). We hypothesize that iTBS will: 1) decrease the behavioral smoking measures described above, which will be explained by a selective 2) decrease in the neural response to cues when individuals 'allow' themselves to crave, and 3) sustain these changes over a time period sufficient to overcome the initial quit attempt (~7-14 days).

Aim 2 (Strategy 2): Modulating the executive system as an approach to treatment: dlPFC iTBS. Aim 2 will follow the design of Aim 1. The procedures will be identical, except iTBS will be delivered to the left dlPFC. We hypothesize that iTBS will: 1) decrease the behavioral smoking measures described above, which will be explained by a selective 2) increase in the neural response to cues when individuals attempt to 'resist' the cues, and again 3) sustain these changes over a similar period as specified in Aim 1.

Exploratory Aim- Evaluate baseline frontal striatal connectivity and discounting rate as factors to predict an individual's likelihood of responding to Strategy 1 versus Strategy 2. We will test the hypotheses that individuals with a higher ratio of (mPFC-striatal)/(dIPFC-striatal) connectivity will be more likely to have a behavioral change after Strategy 1. Various demographics (e.g. gender, smoking history, socioeconomic status, subclinical depressive symptoms, self-efficacy, & motivation to quit will be evaluated as explanatory variables.

The outcomes of the present aims will resolve a critical gap in our knowledge regarding the relative efficacy of 2 promising TMS treatment strategies. These outcomes will be directly translated to a larger longitudinal study evaluating a multipronged approach to improving outcomes in traditional pharmacotherapy or behavioral treatments.

Methods and Measures

Design

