Hypothesis Aim 1: Based on the framework predicted by CNDS theory, and preliminary work (see Study 4), we anticipate that mPFC stimulation will lead to a decrease in brain reactivity to cues during the "allow" condition (passive limbic engagement). We will analyze the neuroimaging data in concert with the behavioral data, evaluating the hypotheses that 1) mPFC iTBS will decrease the brain reactivity to cues in the 'allow' condition (with no consistent link to the 'resist' condition) and that 2) this will be related to the behavioral change in a dose-dependent manner. This will be achieved by extracting the average BOLD signal timecourse and the percent signal change during the CIG versus NEU blocks from a priori anatomically defined regions of interest (ROIs), including the striatum (ventral striatum and dorsal striatum), insula, inferior frontal gyrus, and anterior cingulate cortex. Ventral striatal and dorsal striatal ROIs are derived from the FSL Oxford-GSK-Imanova striatal atlas, mapped via probabilistic diffusion tractography (109) in agreement with anatomical projection zones from the frontal cortex (1). Hypothesis Aim 2: Based on the framework predicted by CNDS theory, and prior studies of dlPFC stimulation in smokers (4-9), we anticipate that dIPFC stimulation will lead to an increase in executive control circuitry (left dlPFC, posterior parietal cortex) during the "resist" condition (executive engagement). As in Aim 1, we will analyze the neuroimaging data in concert with the behavioral data, evaluating the hypotheses that 1) dIPFC iTBS will decrease the brain reactivity to cues in the "resist" condition (with no consistent link to the "allow" condition) and that 2) this will be related to the behavioral change in a dose-dependent manner. The ROI based outcomes of Aim 2 will be compared with the outcomes of Aim 1 using standard general linear modeling as well as a data-driven hierarchical model (see Integration below). As an experimental control, for both Aims we will also calculate the percent signal change from the primary motor cortex, a region which should not be differentially modulated by mPFC or dIPFC stimulation. Although some studies have used the visual cortex as a control region a recent meta-analysis by our group demonstrated that the visual cortex is typically activated more to drug cues than neutral cues (78). Secondary functional connectivity analysis: Additionally, an exploratory seed-based functional connectivity analysis using psychophysiological interactions (PPIs) will be performed using the TMS stimulated ROIs (mPFC and dlPFC) and the striatal target regions (ventral striatum, dorsal striatum- defined above) as seed regions. These data will be compiled across participants and compared between the mPFC and dIPFC stimulation days. Group analyses will be performed using a random effects model limiting significant clusters to those that meet p<0.05 family-wise error corrected.

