
For the follow-up phase: We will test the hypotheses that behavioral change related to Strategy 1 and 2 will be based on an individual's baseline brain cue reactivity data. We will generate Kaplan-Meier curves of behavioral change for the four groups and compare these with cue-reactivity in the MPFC, insula, cingulate (salience network nodes) and striatum using log-rank tests and consider Cox's proportional hazards model to include covariates. Diagnostics will be performed to verify the assumptions such as homoscedasticity and normality. If it is merited, transformations on the outcomes will be considered. Linear contrasts will be utilized to test the hypothesis of equal effects in the two groups at any given time point. Covariates, such as gender and depression that were used to stratify, will be included.

Exploratory Aim: Evaluate baseline frontal striatal connectivity and discounting rate as factors to predict an individual's likelihood of responding to Strategy 1 versus Strategy 2. Finally, will compare the relative efficacy of Strategy 1 versus Strategy 2 on the behavioral change by constructing a computational model. We will test the hypotheses that individuals with a higher ratio of (mPFC-striatal)/(dlPFC-striatal) connectivity will be more likely to have a behavioral change after Strategy 1. Various demographics (e.g. gender, smoking history, socioeconomic status, subclinical depressive symptoms, self-efficacy, & motivation to quit will be evaluated as explanatory variables. This will be achieved by hierarchical linear modeling (HLM v. 7.0, Scientific Software International, Skokie, IL) of the behavioral variables of interest as well as the BOLD signal change in the striatum (caudate) between smoking and image blocks (e.g., CIG vs. NEU) in 'allow' and 'resist' (behavioral change variables nested within treatment (cTBS, iTBS)).

Analytical Plan

Primary data analysis will be done on the Intent to Treat sample (n=138; 69 per Aim: 46 active, 23 sham). Prior to formal statistical analysis, summary statistics for all variables will be obtained and spaghetti plots will be generated. All behavioral outcome measures will be based on standardized composite scores from the literature. We will also use data reduction techniques (such as factor analysis or principle component analysis) to confirm the applicability of the composite scores in our population. Analyses will be performed for each phase separately.

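### The Exploratory Aim predicts response from a ratio of two connectivity values without naming the metric; if the denominator comes near or below zero, a higher ratio may not rank participants as intended

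*Combined protocol and SAP*

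**What the plan says.** The Exploratory Aim appears under Objectives and again under Outcome Measure(s). Its purpose is to "Evaluate baseline frontal striatal connectivity and discounting rate as factors to predict an individual's likelihood of responding to Strategy 1 versus Strategy 2". The directional hypothesis is that "individuals with a higher ratio of (mPFC-striatal)/(dlPFC-striatal) connectivity will be more likely to have a behavioral change after Strategy 1". On the analysis, the Outcome Measure(s) text says: "This will be achieved by hierarchical linear modeling". Neither place names the connectivity metric or says what happens when the denominator is zero or negative.

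Connectivity is described as a method in one place only, the secondary functional connectivity paragraph under Neuroimaging Outcomes, where an "exploratory seed-based functional connectivity analysis using psychophysiological interactions (PPIs) will be performed". Table 2 lists three sequences: the smoking-cue task, a T1 structural scan and a field map. It lists no resting-state or diffusion run. Tractography is mentioned only as the way the published striatal atlas was built ("mapped via probabilistic diffusion tractography"), not as something measured in participants.

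The one transformation clause concerns outcomes, not predictors: "If it is merited, transformations on the outcomes will be considered". The analysis sample is "n=138; 69 per Aim: 46 active, 23 sham".

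**The concern.** A ratio is a sensible index of relative strength when both terms are positive and the denominator stays well away from zero. A PPI coefficient is a difference in coupling between task conditions. Its null value is zero and it takes either sign, as does a correlation. Once the denominator can be small or negative, the ratio stops meaning limbic relative to executive coupling. A small positive denominator gives a very large value, a small negative one reverses the sign, and two negatives look the same as two positives.

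At stake is the plan's stated test of who responds to Strategy 1 rather than Strategy 2. In a linear model a few extreme ratios carry most of the leverage, so a real predictor could be missed, or an apparent one could rest on one or two people. The Objectives say that the trial's outcomes will feed directly into a larger study, so a clear reading of this hypothesis has some value even though it is exploratory.

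**Working it through.** The plan gives no mean, SD, cut-off or power figure for the ratio, so there is nothing of its own to reproduce. The algebra below needs no assumption beyond signed values. The simulations rest on assumed distributions.

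**1. Algebra.** Let a be mPFC-striatal connectivity, b dlPFC-striatal connectivity, and R = a/b.

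- With a = 0.3, b = 0.1, 0.01 and -0.01 give R = 3, 30 and -30.
- (a, b) = (0.3, 0.1) and (-0.3, -0.1) both give R = 3, although the coupling is opposite.
- The slope of R in a is 1/b. When b < 0, stronger mPFC-striatal coupling lowers R, against the stated direction.

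**2. How often it matters.** Assume a and b are Normal with equal means and SDs, and write m = mean/SD. The share of denominators at or below zero is Φ(-m). The chance of at least one among n = 46 (the active arm in one Aim) is 1 - [1 - Φ(-m)]^46. The table also gives the Spearman correlation between R and the difference a - b (400,000 draws, correlation between a and b from 0 to 0.6).

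| m | b ≤ 0 | at least one in 46 | Spearman(R, a - b) |
|---|---|---|---|
| 0 | 50% | about 100% | 0.00 |
| 0.5 | 31% | about 100% | 0.08 to 0.22 |
| 1 | 16% | about 100% | 0.36 to 0.48 |
| 1.5 | 7% | 96% | 0.66 to 0.72 |
| 2 | 2.3% | 65% | 0.86 to 0.87 |
| 3 | 0.1% | 6% | 0.98 |

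For m from 0 to 2, the single most extreme participant of 46 carries a median of about 57% to 65% of the ratio's sum of squares.

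**3. Illustrative power.** Assumptions: n = 46; SD 0.15 for each connectivity; a and b independent; response correlated 0.4 with a - b; one-arm correlation test at two-sided 5%; detection means significant in the predicted direction.

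The difference has about 80% power at every m. As a check, Fisher's approximation gives atanh(0.4) × √43 - 1.96 = 0.4236 × 6.557 - 1.96 = 0.82, and Φ(0.82) = 0.79.

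| mean connectivity | m | ratio power | difference power |
|---|---|---|---|
| 0 | 0 | about 3% | about 80% |
| 0.10 | 0.67 | about 4% | about 80% |
| 0.20 | 1.33 | about 8% | about 80% |
| 0.30 | 2 | about 24% | about 80% |
| 0.45 | 3 | about 60% | about 80% |
| 0.60 | 4 | about 74% | about 80% |

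The ratio figures move by a point or two between runs. Using ranks of the ratio helps at m = 2 (about 61%) but not near zero (about 27% at m = 1.33 and 5% at m = 0.67). The loss is therefore partly one of ordering and not only of outliers. With n = 36, the post-attrition number given under Sample Size for those receiving mPFC TMS, the difference has about 69%.

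**The case against.** The strongest reply is that the signed metric is an inference. The Exploratory Aim does not name PPI, and the PPI paragraph presents it as a separate secondary analysis for comparing the two stimulation sites, not as a baseline predictor. A seed-to-target correlation from the task runs could come from the same scans and might lie well above zero. This stands. What supports the inference is that PPI is the only method described, a correlation is also signed, and no listed sequence yields a non-negative tract measure.

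A reader might infer that the ratio cannot rank participants at all. The documents do not support that. With a mean at least 3 SDs above zero, the ratio orders people almost as the difference does (Spearman 0.98), and at m = 4 its power is close to that of the difference. How near zero the values lie is not reported. A mean that far from zero seems unlikely for a between-condition contrast, but that is judgement.

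A reader might also take the simulation as proof that the difference is the right biomarker. It is not: the response was generated from the difference, so the difference wins by construction. The test is a one-arm correlation, whereas the Aim needs a predictor-by-strategy comparison within a hierarchical model. Also, 46 is the intention-to-treat active arm, before dropout, motion exclusions and participants without MRI.

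Finally, the Analytical Plan calls for summary statistics first, and the Quality Assurance Plan looks at distributions and allows adjustments. Extreme ratios would be noticed, but no rule is set for them, and ranking does not rescue a mean near zero.

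**Conclusion.** The point holds in a limited form. The plan states a directional hypothesis on a ratio, leaves the metric unnamed, and has no rule for small or negative denominators. If dlPFC-striatal values come near or below zero, the ratio is unstable and not monotone, and a higher value may not mean what the hypothesis intends. That conclusion is algebraic and needs only a signed metric.

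The size is conditional. Against about 80% for the difference, ratio power runs from about 3% at mean/SD of 0 to about 74% at 4, under a mean, SD and effect that are assumptions and with a truth that favours the difference.

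This should not be read as a threat to the trial's main results. The primary behavioural and region-of-interest analyses, the sample size and the allocation do not use the ratio. Severity is minor.

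**What to change.** In both statements of the Exploratory Aim (Objectives and Outcome Measure(s)):

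- Name the baseline connectivity metric and the scan it comes from.
- Replace the ratio with mPFC-striatal and dlPFC-striatal connectivity as two separate predictors, each interacting with strategy. Alternatively, use their signed difference on a common scale: Fisher-z if the metric is a correlation, standardised coefficients if it is a PPI.
- Restate the hypothesis to match. For the difference form: a larger mPFC-striatal minus dlPFC-striatal value predicts more behavioural change under Strategy 1.

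The cost is a wording change; scans and seeds stay the same. The two-predictor form spends one more degree of freedom (about 70% against 80% power in the illustration above). The difference form needs the two values to share a scale, and standardising ties that scale to this sample. Either form changes the stated hypothesis somewhat, so the choice should be recorded before the connectivity data are analysed by treatment group.

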The **competing neurobehavioral decision systems** (CNDS) theory posits that in addiction, *choice* results from a regulatory imbalance between two decision systems (impulsive and executive). These behavioral systems are functionally linked to two discrete frontal-striatal circuits which regulate limbic and executive control (2). **Modulating these competing neural circuits (e.g. either dampening the limbic/impulsive system or amplifying the executive control system), may render smokers less vulnerable to factors associated with relapse.** The scientific premise for the proposed research is that direct modulation of these neural circuits will induce changes in cigarette valuation and brain reactivity to smoking cues. However, the relative efficacy of targeting one or the other systems is unknown. To address this gap we will target the two components derived from the CNDS.

These two frontal-striatal neural circuits - the limbic loop (ventromedial prefrontal cortex (vmPFC)-ventral striatum), and executive control loop (dorsolateral PFC (dlPFC)-dorsal striatum) can be differentially stimulated by theta burst stimulation (TBS), a patterned form of transcranial magnetic stimulation. Continuous TBS (cTBS) results in long term depression (LTD) of cortical excitability and intermittent TBS (iTBS) results in potentiation (LTP) (3). Recent studies by our group have demonstrated that LTD-like cTBS to the vmPFC (Aim 1) attenuates brain activity in the nucleus accumbens ([name] et al. 2015) and salience network (2017). In a collaborative MUSC/VTCRI study, 5 days of vmPFC cTBS reduced the value of cigarettes, preference for immediate gratification, and smoking cue-evoked brain activity (see Preliminary data). Alternatively, other groups have demonstrated that LTP-like stimulation to the dlPFC (Aim 2) decreases cigarette craving and cigarette use (4,5). These studies support the targets specified by CNDS. We will evaluate the relative efficacy of these 2 strategies as novel tools to change smoking-related behaviors and dampen brain reactivity to cues in two double-blind, sham-controlled neuroimaging studies. Our long-term vision is that TBS would be used as an acute intervention enabling individuals to get through

the first week after a smoking quit attempt without relapsing, and transition to more sustainable mechanisms of behavioral change (e.g., medication, cognitive behavioral therapy).

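### The exploratory hierarchical model names only the caudate as its striatal BOLD outcome, although the plan defines ventral and dorsal striatal regions and ties Strategy 1 to the ventral one

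*Combined protocol and SAP*

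**What the plan says.** Three parts of the combined protocol and SAP bear on this.

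- **Objectives.** The two circuits are introduced as "the limbic loop (ventromedial prefrontal cortex (vmPFC)-ventral striatum), and executive control loop (dorsolateral PFC (dlPFC)-dorsal striatum) can be differentially stimulated" by theta burst stimulation. Strategy 1 is presented as acting on the limbic system and Strategy 2 on the executive system.
- **Outcome Measure(s), Neuroimaging Outcomes.** Under Hypothesis Aim 1, signal change between cigarette and neutral blocks is extracted from a priori "regions of interest (ROIs), including the striatum (ventral striatum and dorsal striatum), insula, inferior frontal gyrus, and anterior cingulate cortex". The two striatal regions come from a named atlas. Under Hypothesis Aim 2 the plan adds: "The ROI based outcomes of Aim 2 will be compared with the outcomes of Aim 1". It will do this both with a general linear model and with a hierarchical model, and it refers the reader to a later section called Integration.
- **Outcome Measure(s), Exploratory Aim.** The plan "will compare the relative efficacy of Strategy 1 versus Strategy 2 on the behavioral change by constructing a computational model". The method is hierarchical linear modeling of the behavioral variables and of the "BOLD signal change in the striatum (caudate) between smoking and image blocks", in the allow and resist conditions. The data are nested within a treatment factor whose levels are given as cTBS and iTBS.

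**The concern.** The exploratory model looks at how the two strategies differ, and the plan says each strategy works through a different part of the striatum. A striatal outcome for that model should cover both parts. The one named is the caudate, which is neither of the two regions defined for the neuroimaging analysis, and no reason is given for the change.

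Two things are at stake. First, the BOLD part of the model has no outcome in the striatal node that the plan assigns to the medial circuit, although the Design section expects medial stimulation to be the more efficacious strategy. Second, an analyst has two region definitions to choose from. Because the interim plan releases unblinding codes and analyzes data at each 20% of recruitment, the choice could be made after results have been seen.

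**Working it through.** The point is about definitions, and the plan gives no figure to reproduce. The check sets the passages side by side.

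1. **Striatal node of each circuit (Objectives).** Medial (limbic) circuit: ventral striatum. Dorsolateral (executive) circuit: dorsal striatum.
2. **Regions extracted (Neuroimaging Outcomes).** Ventral and dorsal striatum, with insula, inferior frontal gyrus and anterior cingulate. Both nodes in step 1 are covered.
3. **Regions promised for the hierarchical comparison (Hypothesis Aim 2).** The regional outcomes of the two Aims, so the ventral striatum is included.
4. **Region in the hierarchical model actually described (Exploratory Aim).** Caudate only. This is the only hierarchical model described after the cross-reference, and no section titled Integration appears in the text.

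Steps 3 and 4 disagree. Under step 4, the ventral striatum drops out of the hierarchical model.

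**What this does to one record (assumed values).** Suppose a Strategy 1 participant's ventral striatal response falls from 0.30% to 0.10% and the caudate does not change.

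- Aim 1 regional analysis: 0.10 − 0.30 = −0.20 percentage points, recorded.
- Between-Aim general linear model: the same −0.20 enters.
- BOLD part of the exploratory hierarchical model: 0.
- Behavioral part of that model: unaffected.

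The loss is therefore confined to one component of one exploratory model.

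**Direction.** To say that the caudate favors Strategy 2, one must add that the caudate belongs to the dorsal striatum. The plan assigns the dorsal striatum to the dorsolateral circuit but nowhere states that the caudate is part of it. The omission of the ventral striatum needs no such assumption. The tilt does.

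**Signs of outdated text.** The same sentence nests data within cTBS and iTBS. Aims 1 and 2 in the Objectives, and the TMS Treatment heading, now describe iTBS for both strategies.

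**The case against.** The strongest reply is that little depends on this sentence. The ventral striatum is an a priori region in the Aim 1 analysis, enters the between-Aim general linear model and is a seed in the connectivity analysis. The Exploratory Aim states its efficacy comparison and its responder hypothesis in terms of behavioral change, and caudate signal is an additional outcome. The aim is exploratory. All of this stands, and it limits the point to the BOLD component.

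It also rules out three stronger readings that a reader might infer.

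- **That a ventral striatal effect of Strategy 1 goes unscored in the trial.** It does not, for the reasons just given.
- **That the relative-efficacy comparison or the responder prediction is biased against Strategy 1.** Caudate signal neither enters the behavioral outcomes nor defines a responder.
- **That the bias can be sized by a power calculation.** One could assume that each strategy has the plan's d = 0.8 in its own target and that a fraction f of Strategy 1's effect reaches the caudate. The scored effect is then 0.8f: 0, 0.2 and 0.4 for f = 0, 0.25 and 0.5. A two-sided 5% two-sample t-test with 46 active and 23 sham has power 5%, 12% and 34%, against 87% at d = 0.8. With 36 and 18 (the plan's 108 usable data sets, assumed to split evenly by Aim and 2:1) it is 5%, 10%, 27% and 78%. The documents give no value for f, and a real-versus-sham test within one Aim is not the hierarchical model. These figures do not measure the defect.

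The reply does not remove the mismatch. The plan promises regional outcomes in a hierarchical model, and the only such model described uses a different region.

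**Conclusion.** The plan is inconsistent about which striatal region enters its exploratory hierarchical model. As written, the BOLD component leaves out the striatal node that the plan pairs with the medial circuit. This rests on the text alone, reading Strategy 1 as the limbic-circuit strategy, as the plan labels it. The further statement that the component leans toward Strategy 2 is conditional on treating the caudate as dorsal striatum.

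No numerical size can be attached. The sample size of 138, the 2:1 allocation, the 80% power for d = 0.8 and the primary analyses do not change. This is a minor point and a cheap improvement.

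**What to change.** In the Exploratory Aim paragraph:

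1. Replace the caudate with the two striatal regions defined under Neuroimaging Outcomes, ventral and dorsal.
2. Model and report both regions for each strategy, in the allow and the resist condition.
3. In the same edit, point the Integration cross-reference to the section that describes the model, and replace the cTBS/iTBS treatment label with levels that match two iTBS Aims.

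No particular interaction structure need be imposed. How region enters the model is the analyst's choice, provided that it is written down before further unblinded analysis.

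The cost is SAP wording. Both regions are already to be extracted, so no scan, participant or change in sample size is needed. The downside is one more exploratory BOLD outcome.

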Generalized Self-efficacy scale (GSF)	10	1,6,10,and follow ups	This scale was designed to assess self-efficacy, i.e., the belief that one's actions are responsible for successful outcomes. The scaled score for each question ranges from 1 to 4. Higher scores indicate stronger participant's belief in self-efficacy. Previous studies have demonstrated predictive validity of self-efficacy as baseline predictor of smoking treatment outcome (112).
3. Other neuroima	aging se	equences	
T1 MPRAGE	5	1,10	High-resolution structural scans will be obtained using an inversion recovery 3D spoiled gradient echo (3DSPGR) sequence, 192 slices, voxel size: $1.0 \times 1.0 \times 1.0$, field of view: 256 mm, section thickness: 1.0 mm with no gap, giving an in-plane resolution of 256. This sequence will be used for anatomic overlays of the functional data and spatial normalization to a standard atlas, TMS coil positioning, and subsequent voxel-based morphometry.
Field Map	1	1,10	Field Map calculations allow for offline correction of imaging distortion during post-processing. Field map configurations will include: flip angle $(FA)=60$ degrees, field of view $(FOV) = 192$ mm; voxel size = $3.0 \times 3.0 \times 3.0$ mm, 36 contiguous slices 3.0 mm thick.

TMS Treatment – 10 days (Experiment 1/Strategy 1: iTBS to the mPFC; Experiment 2/Strategy 2: iTBS to the dlPFC)

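### The Exploratory Aim's model uses a cTBS/iTBS treatment factor that does not match the two strategies and names no active/sham term, so it does not isolate response to stimulation

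*Combined protocol and SAP*

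**What the plan says.** Under Outcome Measure(s), the Exploratory Aim evaluates baseline connectivity and discounting rate as "factors to predict an individual's likelihood of responding to Strategy 1 versus Strategy 2", with demographic and clinical variables as further explanatory variables. On method it says "This will be achieved by hierarchical linear modeling (HLM v. 7.0, Scientific Software International, Skokie, IL"), applied to the behavioral variables and to striatal (caudate) BOLD change. The only structure given is "behavioral change variables nested within treatment (cTBS, iTBS").

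Other sections describe the treatment differently:

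- TMS Treatment – 10 days: "Experiment 1/Strategy 1: iTBS to the mPFC; Experiment 2/Strategy 2: iTBS to the dlPFC".
- Objectives, Aim 1: "Cigarette smokers will be randomized to receive 10 days of real iTBS or sham iTBS directed to the mPFC".
- Objectives, Aim 2: "The procedures will be identical, except iTBS will be delivered to the left" dlPFC.

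The Design section runs the Aims one after the other (Aim 1 in Years 1-3, Aim 2 in Years 3-5). The TMS treatment section allocates 2:1 active to sham within each Aim. The Analytical Plan gives 138 participants, 69 per Aim, 46 active and 23 sham.

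**The concern.** The aim needs a model in which the effect of a baseline predictor can differ by strategy and by active or sham stimulation. The sentence that defines the model supplies neither distinction. Its treatment factor is stimulation pattern, whereas the arms as described differ by site and by active or sham. Treatment also appears as a nesting level, although it can have at most two levels.

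What is at stake is the interpretation of the result. Baseline discounting, connectivity or motivation may predict change in any smoker who tries to quit. Without a contrast against sham, such a prognostic association looks the same as response to TMS. The two strategies also recruit in different years, so a difference between them may reflect the period. The concurrently randomised sham groups are the only guard against that, and the model does not name them.

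**Working it through.** The documents give no sample size or detectable effect for this aim, so there is no planned figure to reproduce. The check covers what the stated model can estimate, what pooling sham does, and what a corrected model could detect.

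**Inputs.** Per strategy: 46 active and 23 sham (Analytical Plan). Usable data sets: 108 (Sample Size), taken here as 36 active and 18 sham per strategy, an assumed 2:1 split. Further assumptions: one predictor standardised to SD 1, residual SD 1, and one outcome per person.

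**1. Factor taken literally.** Use four columns: intercept, cTBS indicator, predictor, and their product. If every participant is in an iTBS arm, the indicator and the product are zero throughout. The rank is 2 of 4, so neither a strategy effect nor a strategy-by-predictor effect can be estimated.

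**2. cTBS read as an old name for Strategy 1.** The indicator becomes strategy and the rank is 4 of 4, so the comparison is estimable. Sham is still pooled with active.

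**3. Effect of pooling sham.** Randomisation gives active and sham the same expected predictor distribution, so within a strategy:

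- pooled slope = (46/69) × active slope + (23/69) × sham slope.

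Suppose the slopes differ between strategies by 0.50 in active participants and by 0 in sham:

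- pooled difference = (46/69) × 0.50 + (23/69) × 0 = 0.33.

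A simulation of 4,000 trials gave 0.335. If the prognostic slope also shifts by p between recruitment periods, in active and sham alike, the pooled difference becomes p + 0.33. Only the contrast with sham removes p.

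**4. Model with strategy, arm, predictor and all interactions.** The rank is 8 of 8, so every term is estimable. The variance of a slope in a group of n is 1/n. The detectable slope difference at 80% power, two-sided 5%, is (1.960 + 0.842) × SE:

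| Contrast | SE formula (all randomised) | Detectable, 46/23 | Detectable, 36/18 |
|---|---|---|---|
| Predictor × arm within one strategy | √(1/46 + 1/23) | 0.72 | 0.81 |
| Predictor × strategy, active only | √(2/46) | 0.58 | 0.66 |
| Predictor × arm × strategy | √(2/46 + 2/23) | 1.01 | 1.14 |

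Units are outcome SD per predictor SD. The last column puts 36 and 18 in place of 46 and 23.

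**5. Treatment as a nesting level.** With one level there is no between-level variance to estimate. With two, the variance rests on a single degree of freedom. A factor of this kind belongs among the fixed effects.

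**6. Repeated visits, only if entered with no person effect.** For a between-person term, the design effect is 1 + (m − 1)r and the true error is 2 × [1 − Φ(1.96/√DE)]. The documents give no correlation r for this model, so the values are assumed.

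- One change score per person: DE 1, error 5%.
- Two visits, r = 0.3: DE 1.3, error 8.6%.
- Two visits, r = 0.5: DE 1.5, error 11.0%.
- Two visits, r = 0.7: DE 1.7, error 13.3%.

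**The case against.** The strongest defence is that the parenthetical is a stale label. Preliminary data (Study 2 and the Figure 5 caption) ties vmPFC cTBS to Strategy 1, and the Objectives narrative ties it to Aim 1. The Exploratory Aim paragraph itself says it will compare the two strategies. Strategy was therefore probably the intended factor, and on that reading it is estimable. This stands. A reader might infer that the model can never say who responds to which strategy. That is true only of the literal text.

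A reader might also infer that visits from one person will be treated as independent, with inflated error rates. The text does not say so. It is silent on a participant level, and the Behavioral Outcomes paragraph models within-person correlation for the same outcomes. With one change score per person per outcome there is no inflation from this source. Larger figures would require several differently scaled measures stacked in one model, which no section proposes.

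Nor is this the only relevant model. The follow-up paragraph plans Kaplan-Meier curves for all four groups, with log-rank tests and Cox models, on baseline cue reactivity. The comparison of ROI outcomes between Aims uses general linear modeling "as well as a data-driven hierarchical model (see Integration below"). No section titled Integration appears in the text, so equating that model with this one is inference.

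Finally, the aim is exploratory. That limits the consequence, but none of these arguments supplies the missing active/sham term.

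**Conclusion.** The concern holds in a limited form. The stated factor does not describe the arms given in the Objectives and the TMS treatment section. Even with the label corrected to strategy, a model without an active/sham term mixes prognosis with response to stimulation. It also shrinks a strategy-by-predictor slope difference by one third, assuming the sham slopes do not differ between strategies. With serial Aims it leaves period differences uncontrolled.

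It would go too far to state flatly that nobody receives cTBS. Under Human Subjects Protection, the text on repetitive TMS risks describes continuous theta burst stimulation as matching this protocol. That conflicts with the treatment description, and the passages must be reconciled. This point takes no view on which is right.

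Error rates of 11-13% arise only if two visits per person enter with no person effect and an assumed correlation of 0.5-0.7. They are a conditional risk, not a finding about the plan. The primary real-versus-sham analyses are unaffected.

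**What to change.** Replace the parenthetical with a specified model, one per outcome:

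- Fixed effects: strategy (mPFC or dlPFC), arm (active or sham), the baseline predictor, and all their interactions.
- Baseline value of the outcome as a covariate.
- A participant random effect if more than one visit per person enters. Treatment is not a nesting level.
- Interpretation: predictor × arm within each strategy is the measure of who responds to stimulation.
- A statement that the three-way term compares non-concurrent, non-randomised periods and can detect only about 1.0 to 1.1 outcome SD per predictor SD at 80% power, with the assumptions given.

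Coding strategy by site separates the two strategies without relying on the stimulation label. Separately, reconcile the references to continuous and intermittent stimulation across the document, and either supply the Integration section or remove the pointer to it.

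The cost is SAP wording; the data are already to be collected. The downside is that the plan must state openly that the between-strategy moderation test is imprecise.
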